7.2 Secondary Efficacy Endpoints and Analyses

The results for all secondary endpoints will be presented descriptively.

Sponsor: SpineThera Australia Pty. Ltd

Protocol Number: CLIN-0012-STA01-19

SAP Version and Date: Amendment Final 1.1, 13JUL2022

7.2.1 Mean Worst Daily Leg Pain Score: Proportion of Patients with 50% or Greater Improvement at 14, 30, 90, 120, 150, and 180 Days Post-Dosing

A secondary efficacy endpoint for this study is the proportion of patients with a 50% or greater improvement from baseline in mean Worst Daily Leg Pain score at 14, 30, 90, 120, 150, and 180 days post-dosing in the high dose group compared to placebo and low dose group compared to placebo. The number and percentage of patients experiencing a 50% or greater improvement from baseline in mean Worst Daily Leg Pain score will be tabulated for each treatment group and time point for the mITT population.

7.2.2 Change from Baseline in Mean Worst Daily Leg Pain Score

A graphical display of mean observed Daily Leg Pain values over time by treatment group for the mITT population will be prepared.

7.2.3 Patient's Global Impression of Change

Changes in Patient's Global Impression of Change is a secondary efficacy endpoint for this study, where PGI is assessed using the following 7-point scoring classification:

- Very Much Improved = 1
- Much Improved = 2
- Minimally Improved = 3
- No Change = 4
- Minimally Worse = 5
- Much Worse = 6
- Very Much Worse = 7

Number and percentage for each Observed Patient's Global Impression of Change values (i.e. number and percentage of patients for each rating on the PGIC 7-point scale) will be summarized at each visit for each treatment group in the mITT population. In addition, the number and percentage of patients classified as improved (values of 1, 2, and 3) and the number and percentage of patients classified as not worsened (values of 1, 2, 3, and 4) will be summarized at each visit for each of the three treatment groups for the mITT population.

Listings of Patient's Global Impression of Change values will be provided for the modified intent-to-treat population.

7.2.4 Oswestry Disability Index

Changes in Oswestry Disability Index is a secondary efficacy endpoint for this study. The Oswestry Disability Index will be calculated as:

$$\text{Oswestry Disability Index} = \frac{\text{Total Score}}{\text{Total Possible Score}} \times 100\%$$

For example, if all 10 questions are answered and the total score is 16, then the Oswestry Disability Index = $16/50 \times 100\% = 32\%$. If one question is missed or not applicable, the score is calculated as $16/45 \times 100\% = 35.5\%$.

Sponsor: SpineThera Australia Pty. Ltd

Protocol Number: CLIN-0012-STA01-19

SAP Version and Date: Amendment Final 1.1, 13JUL2022

Observed Oswestry Disability Index values and their change from baseline will be summarized at each visit. The number and percentage of patients for each of the five Oswestry Disability Index categorizations will be tabulated according to treatment group and timepoint in the mITT population.

Oswestry Disability Index interpretation of scores will be assessed as:

- 0% to 20%: minimal disability
- 21% to 40%: moderate disability
- 41% to 60%: severe disability
- 61% to 80%: crippling back pain
- 81% to 100%: these subjects are either bed-bound or exaggerating their symptoms

Listings of Oswestry Disability Index values will be provided for the modified intent-to-treat population.

7.2.5 SF-36 QoL Questionnaire RAND version

The SF-36 QoL RAND survey is listed in Reference, Section 11. Changes in SF-36 QoL RAND version domains are secondary efficacy endpoints for this study. Observed SF-36 QoL domain values and their change from baseline will be summarized at each visit for each treatment in the mITT population. Domains will be calculated as described in Appendix 2. The eight health concepts of SF-36 QoL are:

- Physical Functioning (PF); sum of CRF questions: 3-12
- Role Physical (RP); sum of CRF questions: 13-16
- Bodily Pain (BP); sum of CRF questions: 21-22
- General Health (GH); sum of CRF questions: 1, 33-36
- Vitality (V); sum of CRF questions: 23, 27, 29, 31
- Social Functioning (SF); sum of CRF questions: 20, 32
- Role Emotional (RE); sum of CRF questions: 17-19
- Mental Health (MH); sum of CRF questions: 24-26, 28, 30

Listings of the scored SF-36 QoL RAND version domain values will be provided for all patients. In addition, summary statistics for each of the eight domains will be provided at each visit for each treatment group.

7.2.6 Proportion of Patients with 30% of Greater Improvement at 14, 30, 60, 90, 120, 150, and 180 Days Post-Dosing

The same type of analyses as described in 7.2.1 will be conducted at each time point: 14, 30, 60, 90, 120, 150, and 180 days, but using the proportion of subjects with a 30% or greater improvement from baseline in the pain score.

7.2.7 Time to loss of response

A time to loss of response analysis will be conducted for the subset of patients who have 50% or greater improvement in Mean Worst Daily Leg Pain at Day 14.

Sponsor: SpineThera Australia Pty. Ltd

Protocol Number: CLIN-0012-STA01-19

[figure not shown]
SAP Version and Date: Amendment Final 1.1, 13JUL2022

Loss of response will be defined as observing a <50% improvement from Baseline following the Day 14 visit. If a patient with a response at Day 14 does not meet the definition for loss of response at any time after Day 14, then the patient will be censored as of their last date in the study. Time to loss of response will be calculated in days as follows:

Time to loss of response (days) = [Date of first occurrence of <50% improvement from Baseline following Day 14; Or Date of Withdraw; Or Date of Last known still in the study; Or Date of concomitant medication/procedure/therapy starts after the failure of the rescue medication] – [Date of Day 14 Visit].

Time to a loss of response will be summarized based on Kaplan-Meier methods. The number and percentage of patients identified to have had a loss event and those who were censored will be displayed. The median time to loss of response and its corresponding 95% CI will also be produced. All analyses will be performed by treatment group.

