7.1 Primary Efficacy Endpoint and Analyses

Efficacy assessments will be based on the categorical measure of 50% Responder, defined as a patient with 50% or greater improvement in mean Worst Daily Leg Pain (WDLP) score compared to baseline. The mean WDLP score will be derived from the E-Diary recordings entered by the subjects, [REDACTED]

[REDACTED]

[REDACTED]

[REDACTED]

[REDACTED]

[REDACTED]

[REDACTED]

Incomplete Mean Worst Daily Leg Pain score:

All subjects with 5 or more Worst Daily Leg Pain scores recorded in the 10 days preceding the study visit will be included in the analysis. If a subject has less than 5 scores preceding a visit, the subject will not be included in the efficacy assessment for that particular visit. If that same subject has provided 5 or more scores in the 10 days preceding a later visit, the subject will be included in the efficacy assessment for the later visit.

Early Withdrawal:

If a subject withdraws from the study before their 180 day visit, the subject will be included in analyses up to the time that they either stop attending follow-up visits or their consent was withdrawn.

Rescue Medication:

If a patient has failed rescue medication (defined as taking rescue medication for >14 days, taking rescue medication in more than one episode, or receiving treatment beyond the rescue medication regimen defined in the protocol

then the patient will be deemed a non-responder at all timepoints after exceeding the allowed rescue medication, on the day the second episode of Rescue Medication began, or after receiving the additional treatment. The patient will be included in all subsequent timepoints as a non-responder, whether withdrawn or not.

7.1.1 Mean Worst Daily Leg Pain Score: Proportion of Patients with 50% or Greater Improvement from baseline at 60 Days Post-Dosing (Primary Endpoint)

The number and percentage of patients experiencing a 50% or greater improvement from baseline in mean Worst Daily Leg Pain score (i.e. the number and percentage of 50% Responders) will be tabulated for each treatment group. The primary analysis will descriptively compare the proportions of 50% Responders in each of the three arms. The “study success” criterion is defined as the observed percentage of 50% Responders in the high dose group being at least 10 percentage points greater than the corresponding rate in the placebo group.

Listings of Worst Daily Leg Pain will be provided for the modified intent-to-treat population.

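### Time to loss of response is censored at the last study date, not the last evaluable pain score, so Day 14 responders who stop the diary but stay in follow-up remain event-free in the risk set, up to Day 180

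*SAP*

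**What the plan says.** SAP version 1.1, section 7.2.7, analyses the patients who are 50% Responders at Day 14. The event depends on a measurement: "Loss of response will be defined as observing a <50% improvement from Baseline following the Day 14 visit". Without one, "then the patient will be censored as of their last date in the study". Besides the date of the first loss, the formula for the time variable allows these end dates: "Or Date of Withdraw; Or Date of Last known still in the study", and "Or Date of concomitant medication/procedure/therapy starts after the failure of the rescue medication". None of them is the last visit with an evaluable Mean Worst Daily Leg Pain (WDLP). On the estimator: "Time to a loss of response will be summarized based on Kaplan-Meier methods", with a median and 95% CI by treatment group and the numbers of events and censored patients.

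SAP 7.1 decides when a visit can be judged. With fewer than 5 scores in the 10 days before a visit, "the subject will not be included in the efficacy assessment for that particular visit"; the patient comes back in at a later visit that has enough scores. SAP 5.9 imputes nothing that would fill such a gap in this analysis.

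Two groups have separate handling. SAP 7.1 treats patients who fail rescue, or receive treatment beyond it, as non-responders from then on. Protocol 23.1 has patients who need treatment beyond rescue stop the pain diary.

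**The concern.** A censoring date should be the last time at which the patient was known to be free of the event. Here the event is a fall below 50% improvement, which only an evaluable Mean WDLP can show. Attendance at a visit shows that the patient is in the study, not that the patient is still responding.

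Take a Day 14 responder with too few scores at every later visit, who goes on attending and has no rescue failure. No loss can be observed in this patient, yet the patient stays in the denominator at every later loss time. Each observed loss then produces too small a step, and the curve sits too high. The same happens over a shorter span to a patient who stops the diary and withdraws later.

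Time to loss of response is a named secondary objective and endpoint, and the sponsor hypothesizes durable relief (Protocol 19.2). With 55 patients in three arms the responder subset is small, so one or two such patients can move an arm's median. Unequal diary compliance would distort the comparison between arms.

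**Working it through.** **Plan's own figure.** None is stated for this endpoint. The 94% and 81% power figures in SAP 3.3 concern the responder comparison with 60 per arm and do not bear on this point.

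**Inputs from the documents.** Later visits at Days 30, 60, 90, 120, 150 and 180; time counted from the Day 14 visit; 55 patients randomized 1:1:1, so 55/3 ≈ 18 per arm; assumed active response rate 50% (SAP 3.3).

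**Assumptions.** The documents give no Day 14 responder count, loss rate or diary-stop rate. All of these are assumed below, and nominal visit days are used.

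**Worked arm.** Nine Day 14 responders (50% of 18). Losses at Days 60, 90, 90, 120 and 150; two still responding at Day 180; two with no evaluable score after Day 30 who attend to Day 180. The Kaplan-Meier estimate is the product of (1 − d/n) over loss times, with d losses among n at risk. The two diary stoppers stay in n to Day 180 under the SAP rule and leave after Day 30 under last-evaluable censoring.

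| Day | d | n, SAP rule | S, SAP rule | n, last evaluable | S, last evaluable |
|---|---|---|---|---|---|
| 60 | 1 | 9 | 8/9 = 0.889 | 7 | 6/7 = 0.857 |
| 90 | 2 | 8 | × 6/8 = 0.667 | 6 | × 4/6 = 0.571 |
| 120 | 1 | 6 | × 5/6 = 0.556 | 4 | × 3/4 = 0.429 |
| 150 | 1 | 5 | × 4/5 = 0.444 | 3 | × 2/3 = 0.286 |

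The median is the first time that S is 0.5 or less. Under the SAP rule it is Day 150 (150 − 14 = 136 days). Under last-evaluable censoring it is Day 120 (120 − 14 = 106 days). The difference is 30 days.

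**Range, large sample.** Before each of the six later visits a fraction q of those still reporting stop the diary but stay in the study. Of those who go on reporting, a fraction h lose response at the visit. Stopping is unrelated to outcome.

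- True proportion still responding at Day 180: (1 − h)^6. Last-evaluable censoring returns the same value.
- Under the SAP rule nobody leaves the risk set before Day 180 except through an observed loss, so S(180) is 1 minus the total observed losses: 1 − (1 − q)h(1 − r^6)/(1 − r), with r = (1 − q)(1 − h).
- Example, h = 0.15 and q = 0.10: the true value is 0.85^6 = 0.377. Here r = 0.765 and r^6 = 0.200, so S(180) = 1 − 0.135 × 0.800/0.235 = 0.541 (unrounded intermediates).

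| h | True, and either rule at q = 0 | SAP, q = 0.05 | SAP, q = 0.10 | SAP, q = 0.20 |
|---|---|---|---|---|
| 0.10 | 0.531 | 0.601 | 0.660 | 0.754 |
| 0.15 | 0.377 | 0.465 | 0.541 | 0.662 |
| 0.20 | 0.262 | 0.361 | 0.447 | 0.586 |
| 0.25 | 0.178 | 0.282 | 0.373 | 0.523 |

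The smallest overstatement is 0.601 − 0.531 = 0.070 and the largest is 0.523 − 0.178 = 0.345, so about 7 to 35 points.

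**The case against.** A reader might infer that everyone who stops the diary is counted as responding to Day 180. The documents do not support that. Withdrawn patients end at withdrawal. Patients given further treatment after failed rescue, including those whom Protocol 23.1 tells to stop the diary, have their own end date and are non-responders under SAP 7.1. A patient with a gap becomes evaluable again once a later visit has 5 scores. What remains is the patient who stops for good, keeps attending and has no rescue failure. Such a patient is kept at risk as event-free, not scored as a responder at each visit.

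A reader might also take this curve as the trial's only evidence on duration. It is not: responder proportions are tabulated at every visit to Day 180 and mean pain is plotted over time. The visit tables leave out non-evaluable patients, so they do not carry this error.

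Diary stopping may also be rare. Protocol 23.1 describes an automatic email to the study team when a day's score is missing, and the 5-of-10 threshold tolerates half the scores missing. Parts of SAP 7.1 are blacked out and no text is visible under 7.3, so a sensitivity analysis on this point cannot be excluded. The endpoint is secondary and descriptive, with no hypothesis tests (SAP 4.3), and the listings of pain scores would let a reader see the gaps.

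All of this narrows the point and limits its likely size. It does not change the main rule visible in 7.2.7. A sensitivity analysis would sit beside that rule, and a descriptive median with a confidence interval still has to be estimated from time under observation.

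**Conclusion.** The point holds in a limited form. SAP 7.2.7 takes study participation as the censoring date where it should take the last known response status. If Day 14 responders stop the diary and stay in follow-up without rescue failure, the curve and median are biased towards longer response, up to Day 180. For withdrawn patients the excess runs only from the last evaluable score to withdrawal.

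The size rests on assumed rates: 30 days on the median in the worked arm, and about 7 to 35 points at Day 180 over the range tried. It is zero if nobody stops the diary. No test, error rate or primary result is affected. It should be corrected, because the change is small and the subset is small enough for two patients to matter.

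**What to change.** In SAP 7.2.7:

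- Censor patients with no observed loss and no rescue failure at the last visit with an evaluable Mean WDLP (5 or more scores in the preceding 10 days) that still shows at least 50% improvement. If there is no such visit after Day 14, censor at the Day 14 visit.
- Leave patients who are non-responders under 7.1 through rescue failure or additional treatment on their existing end date. Without this exception, those who stop the diary as Protocol 23.1 directs could be censored before the date that makes them non-responders. The section should also state which of its listed dates are events and which are censoring dates, and that the earliest applies.
- Report the number censored before Day 180 by arm.

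The cost is a short addition to the text and one derivation. The downside is fewer patients at risk late in the curve. Last-evaluable censoring also still assumes that stopping the diary is unrelated to outcome; if patients stop because the pain has returned, or because it has gone, the estimate remains biased, but unmeasured time is no longer credited as response.

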7.3 Sensitivity Analysis

8 PHARMACOKINETICS/PHARMACODYNAMICS

A dexamethasone concentration over time profile for PK population will be plotted over the period from pre-dose sample collection up to 24 hours post to the IMP injection.

All dexamethasone concentrations will be provided in patient data listings for the Safety population. A separate descriptive summary of the dexamethasone concentrations by treatment group at each scheduled visit will be performed on the Safety population. A dexamethasone

Sponsor: SpineThera Australia Pty. Ltd

Protocol Number: CLIN-0012-STA01-19

SAP Version and Date: Amendment Final 1.1, 13JUL2022

concentration over time profile for the Safety population will be plotted over against all scheduled visits from Pre-dose to Day 180 where the data is available.

The analysis of PK and PD data will be described in the Clinical Study Report as there were so few PK patients enrolled.

9 SAFETY

All safety analysis reporting will be based on the Safety Population.

9.1 Adverse Events

Adverse events (AEs) will be recorded from the treatment date until the end of study. AEs will also be assessed for seriousness, severity relatedness, and expectedness. AEs will be considered treatment-emergent if their onset occurs within the on-therapy period. Any missing severity assessments will be assumed to be severe, missing relationship assessments will be assumed to be related, and missing seriousness assessments will be assumed as serious.

An overview of treatment-emergent AEs (TEAEs) will be produced, including counts and percentages of patients with any incidences of: TEAEs, TEAEs related to study treatment (i.e., either definitely, probably, or possibly related), TEAEs related to TF-EI procedure (i.e., either definitely, probably, possibly related or not related), severe or worse adverse events (i.e., either severe, life-threatening, or fatal), TEAEs leading to study withdrawal, serious adverse events (SAEs), and fatal SAEs.

Adverse events will be coded based on the Medical Dictionary for Regulatory Affairs (MedDRA) for reporting by system organ class (SOC) and preferred term (PT) in descending order of overall incidence. For these summaries, patients will be counted once within each SOC and PT.

Summaries of adverse events by SOC and PT will include the following types:

- TEAEs;
- TEAEs related to study treatment (including definitely, probably, or possibly related events, and events with missing relatedness);
- TEAEs related to TF-EI procedure (including definitely, probably, or possibly related events, and events with missing relatedness);
- Severe or worse TEAEs (including severe, life-threatening, or fatal events, and events with missing severity);
- SAEs; and
- TEAEs leading to study withdrawal;

A summary of TEAEs by SOC, PT, and maximum severity will also be prepared. Maximum severity will be based on the following scales:

- Fatal
- Life-Threatening
- Severe
- Missing

Sponsor: SpineThera Australia Pty. Ltd

Protocol Number: CLIN-0012-STA01-19

SAP Version and Date: Amendment Final 1.1, 13JUL2022

- Moderate
- Mild

A comprehensive listing of all AEs will be provided in a by-patient data listing. In addition, the following listings will be provided:

- TEAEs related to study treatment (including definitely, probably, or possibly related events, and events with missing relatedness);
- SAEs;
- TEAEs leading to study withdrawal; and
- Fatal AEs.

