26.1 Adverse Event Definitions

Adverse events will be defined by the NHMRC Guidance: Safety monitoring and reporting in clinical trials involving therapeutic goods (November 2016).

Table 7. Adverse Event Definitions.

Seriousness	
Adverse event (AE)	Any untoward medical occurrence in a patient or clinical trial participant administered a medicinal product and that does not necessarily have a causal relationship with this treatment.
Adverse reaction (AR)	Any untoward and unintended response to an investigational medicinal product related to any dose administered.
Safety Critical Adverse Events	Adverse events and/or laboratory abnormalities identified in the protocol as critical to safety evaluations that should be reported to the sponsor according to the reporting requirements specified in the protocol.
Serious Adverse Event (SAE)/Serious Adverse Reaction (SAR)	Any adverse event/adverse reaction that results in death, is life-threatening, requires hospitalisation or prolongation of existing hospitalisation, results in persistent or significant disability or incapacity, or is a congenital anomaly or birth defect.
Significant Safety Issue (SSI)	A safety issue that could adversely affect the safety of participants or materially impact on the continued ethical acceptability or conduct of the trial.
Urgent Safety Measure (USM)	A measure required to be taken in order to eliminate an immediate hazard to a participant's health or safety.
Severity	
Mild	event requires minimal or no treatment and does not interfere with the participant's daily activities
Moderate	event results in a low level of inconvenience or concern with the therapeutic measures. Moderate events may cause some interference with functioning.
Severe	event interrupts a participant's usual daily activity and may require systemic drug therapy or other treatment. Severe events are usually incapacitating.
Life-threatening	event in which the subject was at risk of death at the time of the event*
Fatal	event that resulted in death
Causality	
relatedness to IMP/Placebo or relatedness to TF-EI procedure	
Definitely related	There is a reasonable possibility that the IMP/Placebo or the TF-EI procedure caused the AE. Reasonable possibility means that there is evidence to suggest a causal relationship between the IMP/Placebo or the TF-EI procedure and the adverse event.
Probably related	
Possibly related	

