The information contained in this document is the property of SpineThera Australia Pty Ltd and may not be reproduced, published or disclosed to others without written authorization.

CLINICAL PROTOCOL

Sponsor: SpineThera Australia Pty Ltd

CLIN-0012-STA01-19 **Revision: 06**
Effective Date: 17 Jun2020

Page: 66 of 76

Not related	There is not a reasonable possibility that the IMP/Placebo or the TF-EI procedure caused the adverse event
Expectedness	
Suspected Unexpected Serious Adverse Reaction (SUSAR)	An adverse reaction that is both serious and unexpected.
Unexpected Adverse Reaction (UAR)	An adverse reaction, the nature or severity of which is not consistent with the Reference Safety Information (RSI)

Life-threatening in the definition of a serious adverse event or serious adverse reaction refers to an event in which the subject was at risk of death at the time of the event. It does not refer to an event that hypothetically might have caused death if it were more severe.

Medical and scientific judgement should be exercised in deciding whether an adverse event/ reaction should be classified as serious in other situations. Important medical events that are not immediately life-threatening or do not result in death or hospitalisation but may jeopardise the subject or may require intervention to prevent one of the other outcomes listed in the definition above should also be considered serious.

If there is any doubt as to whether a clinical observation is an AE, the event should be reported. All AEs must be assessed for seriousness, severity, relatedness, expectedness and timing by a study Investigator (who is also a clinician). All changes to an AE must be documented. AEs characterized as intermittent require documentation of onset and duration of each episode.

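### The SAP 9.1 overview row for procedure-related TEAEs includes events judged not related, so as written it repeats the any-TEAE row

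*SAP*

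**What the plan says.** SAP 9.1 asks for an overview giving "counts and percentages of patients with any incidences of: TEAEs" and then for several subsets of TEAEs. Two of these subsets concern attribution:

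- Study treatment: "TEAEs related to study treatment (i.e., either definitely, probably, or possibly related".
- Injection procedure: "TEAEs related to TF-EI procedure (i.e., either definitely, probably, possibly related or not related".

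Later in the same section, the SOC/PT summaries include "TEAEs related to TF-EI procedure (including definitely, probably, or possibly related events, and events with missing relatedness". A general rule at the start of 9.1 adds that "missing relationship assessments will be assumed to be related".

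The underlying scale is in Protocol 26.1, Table 7, which grades "relatedness to IMP/Placebo or relatedness to TF-EI procedure" as definitely, probably, possibly or not related. The last level is defined as "There is not a reasonable possibility that the IMP/Placebo or the TF-EI procedure caused the adverse event".

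The overview wording is identical in SAP 1.0 and SAP 1.1. The change list in SAP Section 11 does not mention it.

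**The concern.** A row labelled as procedure-related should leave out events judged not to be caused by the procedure. This one explicitly lets them in, while the SOC/PT table with the same label leaves them out. Programmed literally, the two tables would describe different sets of patients under one name, and the overview would overstate how often the injection procedure caused harm.

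This matters because safety is a primary objective of this first-in-human study (SAP 2.1.1), and SAP 2.2.1 lists neurological consequences of the injection among the safety outcomes. Every arm undergoes the procedure, so separating its effects from those of the drug is a real question; Protocol 31.3 names that separation as an aim.

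The overview row is also the only place where 9.1 explicitly asks for one overall patient count of procedure-related TEAEs. That count cannot be rebuilt by adding the SOC/PT lines: "patients will be counted once within each SOC and PT", so a patient with events in two classes appears in both.

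**Working it through.** The plan states no figure to reproduce. The check is a comparison of definitions, followed by the size of the resulting error.

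**Step 1: possible states of one TEAE.** Protocol 26.1, Table 7 gives four levels. A missing assessment makes five states. The table shows which of them each SAP 9.1 definition counts.

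| State | Overview, procedure | SOC/PT, procedure | Overview, study treatment |
|---|---|---|---|
| Definitely | yes | yes | yes |
| Probably | yes | yes | yes |
| Possibly | yes | yes | yes |
| Not related | **yes** | no | no |
| Missing | yes (general rule) | yes (stated) | yes (general rule) |
| Total | 5 of 5 | 4 of 5 | 4 of 5 |

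**Step 2: consequence at patient level.** The overview counts patients with at least one qualifying TEAE. If every TEAE qualifies, a patient qualifies exactly when he or she has any TEAE. The procedure row therefore equals the any-TEAE row, whatever the data. In 2,000 simulated data sets of 55 patients the two counts never differed, as the logic requires.

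**Step 3: size of the error in one arm.** Let n be the patients in the arm and k the patients who have at least one TEAE, all of them judged not related to the procedure. Then

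excess = k / n.

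Arm sizes are not given. SAP 3.1 reports 55 treated patients under 1:1:1 randomization, and 55 / 3 = 18.3, so n is assumed to be 18 or 19. The values of k are also assumptions, because the documents hold no AE counts.

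| k (assumed) | n = 19 | n = 18 |
|---|---|---|
| 0 | 0 | 0 |
| 1 | 1/19 = 5.3 points | 1/18 = 5.6 points |
| 3 | 3/19 = 15.8 | 3/18 = 16.7 |
| 5 | 5/19 = 26.3 | 5/18 = 27.8 |
| 10 | 10/19 = 52.6 | 10/18 = 55.6 |

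**Step 4: illustration over all arms.** Suppose 40 of 55 patients have any TEAE. The row as written reads 40/55 = 72.7%, however many events are procedure-related. If 5, 10 or 20 patients have a procedure-related TEAE, the correct entry is 5/55 = 9.1%, 10/55 = 18.2% or 20/55 = 36.4%. All of these counts are assumed.

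**The case against.** The strongest reply is that this is a drafting slip with little reach. The label says related, the SOC/PT bullet a few lines below gives the intended definition, and a careful programmer would notice. No hypothesis is tested, the SOC/PT table and the by-patient AE listing stay correct, and the procedure-related SAE outcome in SAP 2.2.1 is not derived from this row. All of that is true. It limits the weight of the point but does not make the definition right.

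A second reply is that the author may have meant to display the four causality levels as separate lines. The text does not support this: it defines a single category, headed as related, in a list of patient counts. The mock shells are a separate document (SAP Section 1) and were not available, so their layout is unknown. For the same reason it cannot be ruled out that the SOC/PT shell has a line for any event, which would supply the overall count.

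Third, only the SOC/PT bullet concerns the same quantity. The study-treatment row deals with a different attribution, so its difference is one of form. This is correct; the direct contradiction is with the SOC/PT bullet.

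Fourth, the percentages rest on assumed k and n. The Safety population is grouped by treatment received and includes halted or failed procedures (SAP 6.1), so real denominators may differ from an even split of 55. This also stands. The table in Step 3 shows how the error scales and does not predict its size.

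**Conclusion.** The concern holds. As written, the procedure row in the SAP 9.1 overview is the any-TEAE row under another name, and it contradicts the SOC/PT summary of the same quantity. This follows from the Protocol 26.1 scale and the missing-data rule in SAP 9.1, and needs no assumption about the data.

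The numerical effect does depend on the data. It is zero in an arm where every patient with a TEAE has at least one that is procedure-related or unassessed. Otherwise, with 18 or 19 patients per arm, it is about 5 to 6 percentage points for each patient whose TEAEs are all unrelated. The fault is confined to one summary row, so it should be corrected before the tables are programmed, but it does not undermine the rest of the safety analysis.

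**What to change.** In the overview sentence of SAP 9.1, remove the words that admit unrelated events and put *or* before *possibly*. The procedure row then covers definitely, probably, or possibly related events, in the same form as the study-treatment row. Missing relatedness needs no extra text, because the general rule in 9.1 already counts it as related; the row will then match the SOC/PT summary. Confirm that the mock shell for the overview table uses the same definition.

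The cost is three words deleted, one inserted and one shell checked. No data collection or other analysis changes, and there is no downside.
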